4. STUDY POPULATION

4.1 Target population

Inclusion

- Adults (aged ≥18 years).
- Patients undergoing elective or urgent cardiac surgery through a sternotomy and will be receiving CR, as part of the standard clinical pathway.
- Patients capable of giving informed consent.
- Patients capable of completing, and willing to complete, the ISWT.

Patients who are taking part in other research studies can still enter the trial as long as the first study does not include an intervention or element that may affect the FARSTER-care trial

outcomes or would be overly burdensome for patients.

Exclusion

• Patients with postoperative sternal wound complications such as sternal instability.

• Patients with postoperative complications requiring further specialised care, such as

stroke rehabilitation or regular dialysis.

These postoperative complications would interfere with their ability to undertake exercise-

based CR or require long periods of treatment so it would not be possible to randomise

patients with these complications in the times set out in the study.

4.2 Study sites

The trial will recruit cardiac surgery participants from NHS Cardiothoracic Surgery Units within

the UK and linked third party community exercise partners commissioned by the NHS. A

record of all study sites will be maintained by the trial management team and held in the trial

master file.

5. PARTICIPANT RECRUITMENT

5.1 Identification and consent of potential participants

All patients aged 18 years and over who are undergoing planned (elective or urgent) cardiac

surgery with a sternotomy will be screened by the research team at the recruiting NHS sites.

Prospective participants will be given the Patient Information Sheet (PIS) in clinic or at

hospital admission by a Research Nurse (RN), who will also explain the research.

5.2 Consent process

Patients who are interested in taking part in the trial can be approached for informed consent

[figure not shown]
pre- or post-surgery. Patients who consent pre-surgery will be asked to reconfirm their

consent post-surgery. The RN will obtain written informed consent according to Good Clinical Practice (GCP) guidelines. Specific consent will be sought to enable the sharing of identifiable data with York Trials Unit (YTU) as part of the study to facilitate the collection of outcome data. Those who develop complications that will exclude them from the study can be excluded after consenting. Basic data will be collected for those not willing to provide informed consent. The patient pathway is outline in Figure 1.

All patients will undergo surgery as normal and receive standard in-hospital postoperative care.

5.2 Screening for eligibility

Following their surgery, patient eligibility will be confirmed by the clinical team. An *Eligibility Screening Checklist* will be completed and for those patients deemed ineligible, reasons for their ineligibility (including not willing to provide consent) will be recorded anonymously. Screening for complications that would render a patient ineligible can be done anytime during the hospital stay, before randomisation. Patients will be screened against the inclusion and exclusion criteria in Section 4.1.

FARSTER-care Protocol IRAS reference: 334434

V2.0_22.10.2024 ISRCTN: 12204742 6. BASELINE DATA COLLECTION

Prior to randomisation all consenting patients will undergo baseline assessment, including a

questionnaire and clinical assessments. The Participant Baseline Questionnaire will include

patient demographics, and questionnaires related to the secondary outcomes. An

appropriately trained member of the research team at the site will carry out baseline

assessments. Data will be recorded in the Clinician Baseline Form.

7. RANDOMISATION

Following the completion of all baseline measures, the research team at the site will arrange

randomisation. Consenting participants will be randomised 1:1 to the FARSTER-care

(intervention arm) or standard care (control arm) group using block randomisation stratified

by site. The allocation schedule will be generated by a trial statistician not otherwise involved

in the recruitment or randomisation of patients, and implemented via a central, web-based

randomisation system designed and managed by the YTU. Sites will be provided access to the

randomisation system which will automatically send the research team at the site and the

trial team at YTU the treatment allocation. The research team can then inform the participant

of their allocation.

Intervention arm: Participants will have a post-operative outpatient specialist review three

weeks after hospital discharge, followed by commencement of CR from four weeks.

Control arm: Participants will have a post-operative outpatient specialist review six weeks

after hospital discharge, followed by commencement of CR from eight weeks.

All appointments will be made as near as possible to the timescales defined in this protocol.

The RN at each site will ensure that the patient's outpatient review appointment and CR are

arranged at the correct timings. This information will be conveyed to the YTU.

Appointments that are not arranged within 10 days (before or after) of the stated timepoint

will constitute a protocol deviation. If a participant does not attend an arranged appointment,

FARSTER-care Protocol

V2.0_22.10.2024 ISRCTN: 12204742 then this will not constitute a protocol deviation, although the relevant information should be recorded.

8. POSTOPERATIVE OUTPATIENT SPECIALIST REVIEW

A specialist clinical staff member at the recruitment site will perform a face-to-face or remote (with telephone or video call) outpatient review. Postoperative history, medication review and clinical assessment, including for sternal stability, will be done and patients certified fit for CR. This review will take place three weeks after hospital discharge from surgery in the FARSTER-care group, and six weeks in the standard care group. Data will be recorded in the *Outpatient Review Form*.

Participants considered unfit for CR will be given a further review appointment for approximately one week later, the reason(s) documented and the relevant pages of their *Outpatient Review Form*. If following this further review, the participant is deemed fit, they will start their CR. If the participant fails this second review, they will be given another review appointment for two weeks later, the reason(s) documented and the relevant pages of their *Outpatient Review Form*. If following this third review, the participant is deemed fit, they will start their CR. If they fail, they will be deemed unfit for CR and not take part in CR as part of the study but will continue to be monitored as per usual practice. However, they will be sent all participant questionnaires stated in the PIS to complete by trial team at YTU.

9. INITIAL CARDIAC REHABILITATION APPOINTMENT (PRE-CR TIMEPOINT)

Participants referred for CR will be offered a comprehensive programme including an assessment carried out at their initial cardiac rehabilitation appointment, prior to starting their programme in line with the recruiting sites' policies. The initial appointment will take place as near as possible to four weeks post-hospital discharge in the FARSTER-care group and as near as possible to eight weeks post-hospital discharge in the standard care group.

This appointment will be a face-to-face appointment where the participant will perform the ISWT and will be provided with advice on cardiac risk factor reduction. This will typically include information on medication, diet, exercise, and physical activity as well as psychosocial wellbeing and smoking cessation. Participants will be offered further education sessions on

cardiac risk factor reduction during the programme. These would be delivered by specialist CR staff. Referral to other healthcare professionals such as specialist counsellors, pharmacists and dieticians may also be considered if necessary. Unless contraindicated, referral to the exercise component of the CR programme will be made. Following this initial assessment, participants will be enrolled in exercise programmes. Data from the initial CR appointment will be recorded in the *Clinician Pre-CR Form*. If a participant does not attend this appointment, they will be sent another appointment.

During this appointment, participants will be asked to complete PROM-CR, EQ-5D-5L, GAD-7 and resource use questions (*Participant Pre-rehabilitation [control or intervention] Questionnaire*). If required, the trial team at YTU may send this questionnaire to the participant, either electronically or by post.

10. CARDIAC REHABILATION SESSIONS

Participants who have been certified fit for CR will be offered a comprehensive programme organised by the recruiting site. As this is a pragmatic trial, CR exercises will be performed either at designated centres, in patient's homes or a combination of both (hybrid), according to the usual practice of the recruiting centre and the participant's preference.

The participants and the CR team will keep records of attendance and participation in the exercise sessions, including whether the session was centre-based or home-based. Each session will be recorded in either the *Participant Exercise Session Form* or the *Clinician Exercise Session Form*, depending on whether the participant or a member of the CR team are completing the form.

Centre-based CR:

Exercise training will be performed in a gym-like environment with other patients (these are general CR sessions so could include patients not in the trial). Interval circuit training is the most commonly prescribed form of exercise with each individual exercise programme tailored to patients' specific needs and fitness level. The following equipment may be used: heart rate monitors, treadmill, static bikes, and hand weights (alternative/ additional equipment can also be used if required).

FARSTER-care Protocol IRAS reference: 334434

V2.0_22.10.2024 ISRCTN: 12204742 **Home-based CR:**

Home-based CR may be completed instead of centre-based CR and will be undertaken in line

with standard clinical practice at each site. This will include remote monitoring by CR

professionals and measures for safe home exercising. Participants will be made aware of

adverse signs and symptoms and when to stop exercising or call for help [45]. Pulse oximeters

may be provided to participants by sites for use during home exercise sessions. Home

exercise programmes may be provided to patients using software such as Physiotec

(https://physiotec.ca) or the myHeart App (https://mymhealth.com/myheart). Any home-

based CR will follow the local CR delivery team pathway.

Hybrid-CR delivery:

CR delivery teams may be able to support patients who wish to have a combination of centre-

and home-based CR to ensure continuity and progression through the CR programme. After

their exercise testing and prescription, the patients would agree a programme with the CR

team. With fore-planning, this will easily be achieved, but when a sudden change in

circumstances impose the need for an unplanned switch from one mode to the other, then

this will be accommodated as much as possible by the local CR delivery team.

11. CARDIAC REHABILITATION PROGRAMME COMPLETION (POST-CR

TIMEPOINT)

Following completion of the CR programme, at around 16 weeks post-hospital discharge for

control arm and twelve weeks post-hospital discharge for intervention arm, all study

participants will attend an appointment and have a repeat ISWT with data recorded in the

participant's Clinician Post-CR Form. A discharge letter will be sent to patients' General

Practitioner (GP) summarising their treatment. If a participant does not attend this

appointment, they will be sent another appointment.

During this appointment, participants will complete PROM-CR, EQ-5D-5L and GAD-7 questions

(Participant Post-rehabilitation [control or intervention] Questionnaire). If required, the trial

team at YTU may send this questionnaire to the participant, either electronically or by post.

FARSTER-care Protocol IRAS reference: 334434

V2.0_22.10.2024 ISRCTN: 12204742

12. SIX MONTH FOLLOW-UP

About six months (26 weeks) after randomisation, all study participants will attend clinic to have an end-of-study consultation with a member of the research and/or the CR team. All study participants will undergo a final ISWT at this visit. Postoperative history including hospital attendance after discharge, clinical examination including sternal stability, and measurement of vital signs will be undertaken (see Figure 2: Study assessment schedule). Medical records will be checked for hospital readmissions and Accident & Emergency department attendance for surgery-related complications. Clinical data will be recorded on the *Clinician 6-month (Final) Form.* If a participant does not attend this appointment, they will be sent another appointment.

During this appointment, participants will complete PROM-CR, EQ-5D-5L, GAD-7 and resource use questions (*Participant 6-month Questionnaire*). If required, the trial team at YTU may send this questionnaire to the participant, either electronically or by post.

13. TWELVE MONTH FOLLOW UP

About twelve months (52 weeks) after randomisation, all study participants will be invited to complete EQ-5D-5L, GAD-7, and NHS resource use, costs, and time off work questions (*Participant 12-month Questionnaire*). The trial team at YTU will manage the follow-up at this timepoint. Participants can opt to complete the questionnaire electronically, by post or by telephone.

Figure 2: Study assessment schedule

	Baseline			Post-randomisation				
	Pre- surgery	Post- surgery	Outpt. review	Pre- CR	CR	Post -CR	6m FU	12m FU
Screening for eligibility		Χ						
Consent	X	Χ						
Baseline data collection		Χ						
Randomisation		Х						
Clinical assessment		X*	Χ*				Χ	
ISWT				X*		Χ*	Χ	
PROM-CR				Х		Х	Х	
EQ-5D-5L		Х		Х		Х	Χ	Х
GAD-7		Χ		Х		Х	Χ	Х
CR assessments				X*		Χ*		
Vital signs – heart rate, blood pressure, oxygen saturation		X*	X*	X*		X*	Х	
CR session logs					Х			
Resource use questions				Х			Χ	Х
Adverse event monitoring			X*	Х		Х	Х	Х

^{*}part of normal patient pathway

14. LEVEL OF BLINDING

By the nature of the timing of the study treatments used within this study, blinding of the participants and clinicians is not possible and procedure for un-blinding is not necessary.

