3. STUDY DESIGN

The study design has been informed by the results of a feasibility study (FARSTER) [39], which

demonstrated that it would be acceptable and feasible to undertake a full-scale trial, subject

to some modifications to maximise recruitment. The objectives of FARSTER-care will be

addressed using a multi-centre, two arm, parallel group, open RCT, including an internal pilot

study and embedded health economic analysis. The trial will recruit 588 cardiac surgery

participants who have had a sternotomy at UK centres over 24 months and will randomise

participants 1:1 to the FARSTER-care (intervention) or standard care (control) arms.

Participants in the intervention arm will have specialist outpatient review at three weeks after

hospital discharge, followed by commencement of CR from four weeks. Participants in the

standard care arm will receive standard post-sternotomy cardiac surgery care which includes

specialist outpatient review at six weeks after hospital discharge, followed by commencement

of CR from eight weeks.

At the start and end of CR, and again at six months post-randomisation, participants will

undergo fitness testing using the ISWT during face-to-face appointments. Clinical data will be

recorded at baseline and appointments up to six months post-randomisation. Participants will

be asked to self-report outcome data by completing questionnaires from baseline up to

FARSTER-care Protocol IRAS reference: 334434 V2.0 22.10.2024

twelve months post-randomisation. The study flow chart (Figure 1) and study assessment schedule (Figure 2) detail the study timelines.

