3.1 Internal Pilot Study

The first eight months of recruitment will constitute an internal pilot phase, after which progress will be assessed against pre-specified criteria using a traffic light system (red/amber/green) (Table 1). The outcome of the pilot study will enable a confirmation of whether the trial is feasible and determine progression to the main trial. The criteria assessed relate to the recruitment of sites and participants, deliverability of the intervention, and rate of follow-up for the primary outcome. The recruitment rates and number of sites open are based on the projected recruitment targets for the 24-month recruitment period. Results will be compared against the study's recruitment assumptions and progression targets, and continuation of the trial or relevant modifications will be decided by the Trial Steering Committee (TSC) and the funding body.

Table 1. Internal pilot progression criteria.

	Red	Amber	Green
Recruitment rate/site/month	<1	1-1.9	≥2
Number of sites opened	<5	5-7	≥8
Collection of ISWT at the post-CR timepoint	<60%	60-84%	≥85%
Adherence with intervention pathway (difference between average	<2	2-3	3+
time between surgery and CR between the two groups in weeks)			

The actions taken for the progression criteria are outlined below:

- Green: continue the trial.
- Amber: review procedures to identify underlying problems, and put in place strategies
 to address these, review after an interval and if recruitment trajectory does not
 indicate that full recruitment will occur within scheduled recruitment period, discuss
 next steps with TSC and funder.
- Red: terminate the trial unless we can confidently identify successful strategies or rapidly resolve the problem.

FARSTER-care Protocol IRAS reference: 334434

V2.0_22.10.2024 ISRCTN: 12204742 3.2 Outcomes

Primary outcome

The primary outcome is the difference in ISWT (meters walked) between the treatment

groups at six months post-randomisation. The ISWT is a functional capacity test used to

measure physical fitness and is widely used in CR programmes in the UK [40]. Participants will

be asked to perform this test before their CR commences (pre-CR time point), once CR

finishes (post-CR time point) and at the six-month time point.

Secondary outcomes

Secondary outcomes will be collected at baseline, pre-CR, post-CR, six- and twelve- months

post-randomisation (see Figure 2: Study assessment schedule). The secondary outcomes

include:

Physical health

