YTU will also manage the participant-reported data collection at the Pre- and Post-CR timepoints for participants who do not attend CR (if they are not deemed as fit for CR following the Outpatient Review or if they withdraw from CR by completing a Change of Status). As and when required, YTU may also send questionnaires to participants at other timepoints to support clinical teams.

To promote attendance at the six-month follow-up, during which visit the primary outcome measure is collected, participants will be sent a newsletter to optimise their engagement with the trial. Participants will also be offered £10 for completing their six-month follow-up, to cover for any travel costs. To enhance response rates of the twelve-month follow-up which consists of a participant questionnaire, participants will be sent a postcard thanking

them for their ongoing participation and support of their trial. YTU will coordinate the distribution of these documents.

Table 2. Data collection

Visit	Timepoint	Completed by	Site responsible	CRF capturing data
Eligibility	Prior to hospital discharge at week 0	Specialist clinical staff	Recruiting site	Eligibility Screening Checklist
Baseline	Prior to hospital	Specialist clinical staff/RN	Recruiting site	Clinician Baseline Form
baseiiile	discharge at week 0	Participant	Recruiting site	Participant Baseline Questionnaire
Outpatient review	6 weeks (control) or 3 weeks (intervention)	Specialist clinical staff	Recruiting site	Outpatient Review Form
	Queaks (control) or	Specialist CR staff	Recruiting or CR site	Clinician Pre-CR Form
Initial CR appointment	8 weeks (control) or 4 weeks (intervention)	Participant	Recruiting or CR site	Participant Pre-rehab Questionnaire (control/ intervention)
CR sessions	One or two times a week between 8 to 16 weeks (control) or 4 to 12 weeks (intervention)	Participant OR Specialist CR staff	Recruiting or CR site	Participant Exercise Session Form or Clinician Exercise Session Form
CR	16 weeks (sentral)	Specialist CR staff	Recruiting or CR site	Clinician Post-CR Form
programme completion	16 weeks (control) or 12 weeks (intervention)	Participant	Recruiting or CR site	Participant Post- rehab Questionnaire (control/ intervention)
6-month follow-up	26 weeks	Specialist clinical staff/specialist CR staff/RN Participant	Recruiting or CR site Recruiting or	Clinician 6-month (final) Form Participant 6-month
		·	CR site	Questionnaire
12-month follow-up	52 weeks	Participant	YTU	Participant 12-month Questionnaire

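### The protocol does not say whether the person running the six-month ISWT, the sole primary outcome, may know the allocation, and it allows that person to be the participant's own CR therapist

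*Protocol*

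**What the plan says.** Section 3 describes the design as "addressed using a multi-centre, two arm, parallel group, open RCT, including an internal pilot" study. Section 3.2 fixes the primary outcome: "The primary outcome is the difference in ISWT (meters walked) between the treatment" groups at six months after randomisation.

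Section 14 is a single sentence. Because the arms differ in timing, "blinding of the participants and clinicians is not possible and procedure for un-blinding is not necessary". It names participants and clinicians, and says nothing about whoever measures the outcome.

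Section 12 has the six-month visit, with its final ISWT, conducted by "a member of the research and/or the CR team". Table 2 in Section 17.1 lists who may complete the clinician form for that visit: "Specialist clinical staff/specialist CR staff/RN", at a recruiting or a CR site. Neither place sets a condition on involvement in the participant's care or on knowledge of allocation.

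Section 7 describes a "randomisation system which will automatically send the research team at the site and the" trials unit the allocation. It adds: "The RN at each site will ensure that the patient's outpatient review appointment and CR are" arranged at the times that belong to the allocated arm.

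Two provisions bear on measurement quality. Section 17.1 requires calibrated equipment and standard site procedures, and Section 17.3 requires training in functional outcome measures. Neither mentions allocation or encouragement during the test.

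**The concern.** The ISWT is a supervised performance test, and its result in metres is the whole primary outcome. The tester may be the therapist who knows when that participant started CR. Expectation could then affect how the test is conducted, in a trial whose rationale (Section 1) favours earlier CR. A larger sample does not remove such a bias, and an analysis plan cannot repair it, because it arises when the outcome is collected.

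The reason given in Section 14 does not extend to every possible tester. Timing reveals the arm to those who book or deliver the pathway. By 26 weeks it need not reveal it to anyone else.

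**Working it through.** **Could a tester at 26 weeks be unaware of the arm?**

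- Planned CR ends about 12 weeks (intervention) or 16 weeks (control) after discharge (Section 11, Table 2).
- Under Section 8, two failed fitness reviews add about 1 + 2 = 3 weeks. The later planned finish is then about 16 + 3 = 19 weeks, still before week 26.
- The pre- and post-CR questionnaires come in separate control and intervention versions. The six-month form and questionnaire do not (Sections 9, 11 and 12, Table 2).

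So on the planned schedule neither ongoing CR nor the paperwork reveals the arm at six months.

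**Who among the authorised staff would know it anyway?**

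- CR staff know it if they delivered that participant's CR (Sections 9 and 10).
- Specialist clinical staff know it if they carried out the outpatient review, at three or six weeks (Section 8).
- The research team and research nurse receive the allocation, and the nurse arranges the arm-specific appointments (Section 7).
- Any tester may learn it at the visit. Section 12 combines the ISWT with postoperative history and a records check, Figure 2 adds adverse-event monitoring, and the participant knows the arm.

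Excluding only those who delivered the review or CR is therefore not enough. At many sites it would point to the nurse, who knows the arm.

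**The protocol's sample size (Section 18.1)**

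Inputs: standardised effect 0.3 (52 m on an SD of 174 m), 90% power, 5% two-sided, 20% attrition, 1:1 allocation.

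- Normal approximation: n per arm = 2 × (1.960 + 1.282)² / 0.3² = 233.5, so 234; 468 / 0.8 = 585.
- Two-sample t-test: 234.46, so 235 per arm; 470 / 0.8 = 587.5, so 588.

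The stated 588 is reproduced, with about 235 completers per arm.

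**Illustration of tester bias**

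The documents give no figure for tester bias, so the values of b below are assumptions. The true effect is set to zero.

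- SE = 174 × √(2/235) = 16.05 m
- P(reject) = 1 − Φ(1.96 − b/SE) + Φ(−1.96 − b/SE)

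| Assumed b (m) | b / 52 m | b / SE | Two-sided type I error |
|---|---|---|---|
| 0 | 0% | 0 | 5.0% |
| 5 | 10% | 0.31 | 6.1% |
| 10 | 19% | 0.62 | 9.6% |
| 20 | 38% | 1.25 | 23.8% |

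This SE is for an unadjusted comparison and uses the planning SD, which is a pre-CR value. If the planned covariate-adjusted model has a smaller SE, the same bias would inflate the error more; a larger six-month SD would have the opposite effect.

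**The case against.** The strongest case on the other side has five parts.

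- **The statement in Section 14 is true.** A reader might infer that the protocol declares assessor blinding impossible. It does not: it names participants and clinicians, and for them the statement is right. The fault is an omission.
- **Masking is harder than it looks.** A reader might infer that a masked tester is readily available among the three authorised roles. The documents do not support that. Section 7 informs the research team and the nurse, the other roles deliver the arm-specific care, and the visit itself can reveal the arm. No staffing figures are given, and community CR sites may have nobody uninvolved. This stands, and it shapes the fix.
- **The bias figures are hypothetical.** Neither size nor direction comes from the documents, and the protocol does not describe how the ISWT is administered or ended. This stands.
- **Training and standard procedures help.** They support consistency, but they do not restrict knowledge of allocation or encouragement, so they answer the point only in part.
- **The trial is open and pragmatic.** Participants' own effort stays unblinded whatever is done. This is true, and it means that only the tester's share of the bias can be avoided.

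**Conclusion.** The point holds as a gap. The protocol is silent on whether the six-month tester may know the arm, permits the treating therapist to test, and does not mask research staff by default. The timing reason in Section 14 does not justify that silence, because on the planned schedule both arms have finished CR well before week 26.

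The size cannot be established from the documents. With an SE of about 16 m, assumed differential tester effects of 5, 10 and 20 m give type I errors of about 6%, 10% and 24%. A reader should not take any of these as the trial's actual error rate.

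This does not invalidate the trial, and the sample size and power are unaffected. It is an inexpensive improvement to how the sole primary outcome is collected. It has to be made in the protocol and trial procedures, since a SAP cannot later supply masking or recover an awareness record that was never made.

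**What to change.** In Sections 12 and 14, state that, where a site's existing staffing allows, the six-month ISWT is run by an already authorised staff member who did not randomise, book, review or deliver CR to that participant. In addition:

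- run the ISWT before history-taking and the records check, leaving any safety check a site already makes before an exercise test as it is;
- ask the participant not to disclose the arm, and keep allocation off the test worksheet;
- use the same fixed ISWT instructions, with no added encouragement, for everyone;
- record whether the tester knew the allocation.

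Report, by arm, the proportion of tests run by aware and unaware testers. Any analysis by that flag should be descriptive only. Awareness arises after randomisation, is not randomised, and probably tracks site size and CR attendance, so a difference by flag could not be read as tester bias.

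The cost is some scheduling effort, a fixed script and one item on the form, with no new staff required. Small or community CR sites will often have to record that the tester was aware, and participant effort stays unblinded.
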